# 6.1.7. Mini International Neuropsychiatric Interview (M.I.N.I.)

The M.I.N.I. is a clinician-rated diagnostic assessment that will be administered at Screening and will be considered a source document. The M.I.N.I will be administered by an Investigator or other individual that is suitably qualified by education or training. See APPENDIX 9 for a sample M.I.N.I. assessment.

## **6.2.** Blood Volume Collected

The total volume of blood withdrawn, including the volume required for screening, on-study and post-study tests, should be approximately:

- 166 mL for Part A SAD Phase (Cohorts A1, A2, A4, and A5)
- 250 mL for Part A SAD Phase (Cohorts A3 [Food-Effect Cohort])
- 330 mL for Part B MAD Phase (all cohorts)
- 379 ml for Part C Smoker Phase (all cohorts)

The total blood donation may be higher if repeat blood samples are required for safety assessments.

#### **6.3.** Pharmacokinetic Assessments

Blood samples will be collected (1 tube of 6 mL each) for PK assessments.

For the SAD Phase, blood sampling for PK of SBP-9330 in plasma will be performed at pre-dose (within 60 minutes of dosing) and 0.25, 0.5, 1, 1.5, 2, 3, 4, 6, 9, 12, 24, 36, and 48 hours post-dose ( $\pm 10\%$ ). The food-effect cohort will have identical PK draws in Periods 1 and 2.

For the MAD and Smoker Phase, blood sampling for PK of SBP-9330 in plasma will be done at the following timepoints:

- At pre-dose (within 60 minutes of dosing) and at 0.25, 0.5, 1, 1.5, 2, 3, 4, 6, 9, 12, and 24 hours post-dose (±10%) on Day 1
- At predose (within 60 minutes prior to morning drug administration) on Day 7, 11, 12, and 13
- At pre-dose (within 60 minutes prior to drug administration) and at 0.25, 0.5, 1, 1.5, 2, 3, 4, 6, 9, 12, 24, 36, and 48 hours post-dose on Day 14 ( $\pm 10\%$ ).

Altasciences Project Number: CNO-P5-319

The complete blood sampling schedule is also presented Table 1 (SAD Phase), Table 2 (MAD Phase) or Table 3 (Smoker Phase).

Blood samples will be collected by direct venipuncture into a labeled tube containing the appropriate anticoagulant as specified by the bioanalytical facility. As an option to the subject or if judged necessary by the clinical staff, blood samples may be collected from an indwelling cannula (stylet catheter that requires no flushing), which will be placed in the vein of the subject.

The time of PK blood sample collection will be calculated relative to the time of treatment administration. The actual time of all PK blood draws will be recorded and reported for all subjects.

SBP-9330 concentrations for PK assessments will be obtained through bioanalysis of the plasma derived from the blood samples drawn during this study, using a validated bioanalytical method.

Bioanalysis procedures will be presented in the bioanalytical plan.

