- 6 Serum pregnancy test for all female subjects at Screening and urine pregnancy test, for female subjects of childbearing potential only, at all other timepoints.
- 7 Clinical laboratory tests (including clinical chemistry, lipid profile, coagulation, hematology, and urinalysis): at Screening; on Day -1 (admission); at pre-dose on Days 1, 3, 7, 14, and 16; and at follow-up/EOS.
- Triplicate 12-lead ECG: at Screening; Day -1 (admission); at pre-dose (within 60 minutes) on Day 1 and at 3 hours post-dose on each dosing day (i.e., Days 1 to 14) (±15 minutes); prior to discharge; and at follow-up/EOS.
- When safety and PK blood draws coincide, procedures should be carried out in the following order: (1) ECGs, (2) vital signs, (3) PK blood sampling (nominal), (4) smoking assessments.
- Vital signs: at Screening; Day -1 (admission); at pre-dose (within 60 minutes) and 1.75 hours post-dose on each dosing day (i.e., Days 1 to 14) (±15 minutes); prior to discharge; and at follow-up/EOS. Orthostatic measurements will be obtained at Screening, Day -1, pre-dose, 1.75 hours (±15 minutes), and 3.5 hours (±15 minutes) post dose. For orthostatic measurements blood pressure and pulse rate will be measured after the subject has been in the supine position for at least 5 minutes, repeat measurements will be taken after the subject has been standing in the upright position for at least 2 to 3 minutes (respiratory rate and temperature will be measured with blood pressure and pulse rate in the supine position only).

- Blood sampling for PK of SBP-9330 in plasma: at pre-dose (within 60 minutes of dosing); at 0.25, 0.5, 1, 1.5, 2, 3, 4, 6, 9, 12, and 24 hours post-dose (±10%) on Day 1; within 60 minutes prior to morning drug administration on Day 7, 11, 12, and 13; and within 60 minutes prior to drug administration and at 0.25, 0.5, 1, 1.5, 2, 3, 4, 6, 9, 12, 24, 36, and 48 hours post-dose on Day 14 (±10%).
- 12 Expired breath CO will be measured with a Bedfont SmokerlyzerTM.
- 13 Cotinine samples should be collected within 60-minutes prior to dosing on dosing days.
- A baseline/screening version of the C-SSRS will be used at Screening and a "since-last-visit" version will be used at all subsequent visits where the C-SSRS is administered.

Altasciences Project Number: CNO-P5-319

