## 5.3. Administration of Study Drug

Study drug will be administered in the morning at approximately the same time each day. The date and time of each dose will be recorded. For each subject, all scheduled post-dose activities and assessments will be performed relative to the time of study drug administration.

Each oral dose of the assigned formulation will be administered to subjects with approximately 240 mL of water at ambient temperature. An additional volume of water of up to 150 mL may be provided in 50 mL increments to ensure that the whole dose is administered.

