T_{\max}	Time of maximum observed concentration; if it occurs at more than one time point, T_{\max} is defined as the first time point with this value
C_{τ}	Concentration at the end of the dosing interval. Observed concentration, otherwise the predicted concentration value will be calculated as per Phoenix® WinNonlin®'s built-in rules for interpolation/extrapolation, and subject to the criteria for PK parameters requiring λ_z estimation.
AUC_{τ}	Area under the concentration time curve over the dosing interval at steady state,

	calculated from 0 to 24 hours (dosing interval)
AUC _{0-T}	Area under the concentration time curve from time 0 (dose administration) to the time of last quantifiable concentration (T _{last})
T _{half}	Terminal elimination half-life, calculated as $\ln(2)/\lambda_Z$
T _{half, eff}	Effective half-life, calculated as $\tau * \ln2 / \ln(Rac_{(AUC)} / (Rac_{(AUC)} - 1))$, where τ is 24 hours ¹
CL/F _{ss}	Apparent total clearance at steady state, calculated as Dose/AUC _τ
Vz/F _{ss}	Apparent volume of distribution at steady state, calculated as Dose/ $\lambda_Z * AUC_{\tau}$
C _{max} /D	Dose-normalized C _{max}
AUC _τ /D	Dose-normalized AUC _τ
AUC _{0-T} /D	Dose-normalized AUC _{0-T}
Rac _(C_{max})	Accumulation ratio evaluated by comparing Day 14 C _{max} to Day 1 C _{max}
Rac _(AUC)	Accumulation ratio evaluated by comparing Day 14 AUC _τ to Day 1 AUC ₀₋₂₄

Parts B and C: MAD nonsmoker and smokerPhases, Various Days:

C _{trough}	Observed concentration at the end of the dosing interval (predose concentrations on Days 2, 7, 11, 12, 13, and 14)
---------------------	--

The following PK parameters will be used for PK calculation and presented in the PK listings only

T _{last}	Time of last measurable observed concentration
C _{last}	Observed concentration corresponding to T _{last}
λ_Z	Apparent elimination rate constant, estimated by linear regression of the terminal linear portion of the log concentration versus time curve
λ_Z Upper	Upper limit on time for values included in the calculation of λ_Z
λ_Z Lower	Lower limit on time for values included in the calculation of λ_Z
Number of Points	Number of data points in computing λ_Z
R ²	Goodness of fit for the terminal phase
Residual area	Extrapolated area (i.e., percentage of AUC _{0-∞} due to extrapolation from T _{last} to infinity: [AUC _{0-∞} - AUC _{0-T}] / AUC _{0-∞} * 100)

¹Sources: Gidal et al., 2017 and Boxenbaum et al., 1995

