10 INTERIM ANALYSES AND DATA SAFETY MONITORING

Preliminary blinded “top line” PK results will be generated after each cohort of the SAD and MAD phase for dose selection and safety assessment prior to the next dose escalation.

These preliminary blinded PK results will be performed on SBP-9330 data as outlined in Sections 7.1 through 7.4, with the exception that nominal times will be used in the analysis instead of actual times. Blinded concentration tables, mean and blinded individual plasma concentration-time profiles, blinded PK parameter tables of the key PK endpoints (e.g., C_{max} , T_{max} , and AUCs) will be generated, data permitting.

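### In Parts B and C the ±10% window on the Day 1 24-hour PK sample extends up to 2.4 h past the Day 2 dose, at odds with the SAP's treatment of that sample as predose

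*Protocol*

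**What the plan says.** Protocol 6.3 sets the MAD and Smoker Day 1 sampling as "At pre-dose (within 60 minutes of dosing) and at 0.25, 0.5, 1, 1.5, 2, 3, 4, 6, 9, 12, and" 24 hours; the window reads "and 24 hours post-dose (±10%) on Day 1". The Table 3 PK footnote repeats it ("at 0.25, 0.5, 1, 1.5, 2, 3, 4, 6, 9, 12, and 24 hours post-dose (±10%) on Day 1"), and the Table 2 footnote and SAP Tables 14 and 15 carry the same rule.

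Protocol 5.3 fixes the dose timing: "Study drug will be administered in the morning at approximately the same time each day". No tolerance is given.

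The stand-alone trough samples are tied to the dose, not to the clock: "At predose (within 60 minutes prior to morning drug administration) on Day 7, 11, 12, and 13". The Day 14 predose draw has the same 60-minute rule. Day 2 is not covered, although the Day 1 24-hour draw is the only PK sample that falls on Day 2.

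SAP Table 7 defines Ctrough as "Observed concentration at the end of the dosing interval (predose concentrations on Days 2, 7, 11, 12, 13, and 14". The protocol synopsis and SAP Table 1 list troughs on Days 7, 11, 12, 13 and 14 only.

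Two passages point to other sources for the windows. Protocol Section 6 refers PK collection windows to the unit's SOPs, unless the protocol states otherwise. SAP 5.2 judges sampling-time deviations against a named SOP. Neither document gives the SOP content.

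**The concern.** A symmetric window suits a sample with no dose after it, such as the 24-hour draws in Part A and on Day 14. On Day 1 of Parts B and C a dose follows at about 24 h, so a draw at, say, 25 h meets the stated window and yet contains drug from the second dose.

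That one sample closes Day 1 AUC0-24. This is the denominator of Rac(AUC), and effective half-life is computed from Rac(AUC). The same sample is the first point on the SAP's trough plot. Analysing by actual time, as Protocol 8.4.3 and SAP 7.3 require, corrects the clock but not the concentration. The interim runs in SAP 10 are done "with the exception that nominal times will be used in the analysis instead of actual times", so there a late value would be entered as exactly 24 h.

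**Working it through.** The plan has no figure of its own to reproduce. The check has two parts.

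**1. Window arithmetic (documents only).**
- 24 h × 0.90 = 21.6 h and 24 h × 1.10 = 26.4 h, a width of 4.8 h.
- With the Day 2 dose at 24 h, the part after the dose is 26.4 − 24 = 2.4 h, half of the window.
- Under the 60-minute predose rule used for the other troughs, the window would be about 23 to 24 h and the part after the dose would be 0.

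**2. Size for a subject sampled late (assumption-based).** The documents give no human half-life or absorption rate. I assume one compartment, C(t) = ka/(ka − k) × (e^(−kt) − e^(−ka·t)), with k = ln2/half-life, ka = 1/h, concentrations in units of dose·F/V, and dose 2 at exactly 24.0 h. AUC is linear-up/log-down on the protocol's times. From the documents: Rac(AUC) = Day 14 AUCτ / Day 1 AUC0-24, and effective half-life = 24 × ln2 / ln(Rac/(Rac − 1)), which is undefined when Rac ≤ 1.

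Example: half-life 12 h, draw at 25 h.
- True values: C(12) = 0.531, C(24) = 0.265. Area from 12 to 24 h = 12 × (0.531 − 0.265)/ln(0.531/0.265) ≈ 4.6. AUC0-24 = 12.69.
- Draw at 25 h: 0.251 left from dose 1 plus 0.611 from dose 2 = 0.862, which is 3.3 times the true trough.
- Interpolated to 24 h on actual times: 0.531 + (0.862 − 0.531) × 12/13 = 0.837. Area from 12 to 24 h = 12 × (0.531 + 0.837)/2 ≈ 8.2. AUC0-24 = 16.30, or 16.30/12.69 − 1 = +28%.
- Day 14 AUCτ = 17.28. Rac falls from 17.28/12.69 = 1.36 to 17.28/16.30 = 1.06.
- Effective half-life falls from 12.6 h to 5.8 h.

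Draw at 25 h, ka 1/h:

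| Assumed half-life | Day 1 AUC0-24 | Rac(AUC) | Effective half-life |
|---|---|---|---|
| 8 h | +37% | 1.16 → 0.85 | not computable |
| 12 h | +28% | 1.36 → 1.06 | 12.6 → 5.8 h |
| 24 h | +21% | 2.06 → 1.70 | 25 → 19 h |

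A draw at 24.25 h already gives +8% to +16% for half-lives of 24 to 8 h. Widening the assumptions (half-life 6 to 24 h, ka 0.5 to 2/h, draw at 24.5 to 26.4 h), the error in AUC0-24 runs from about +8% to +60% on actual times and +8% to +65% on nominal times.

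**3. Effect on a cohort.** Each cohort has 8 active subjects. One late draw in the 12-hour example moves the geometric mean AUC0-24 by 1.284^(1/8) − 1 ≈ +3%.

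**The case against.** The other side has a good deal to say, and most of it limits the point without removing it.

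- **SOPs.** The governing window may be narrower than ±10%. The content is not given, so this cannot be excluded. But Protocol Section 6 gives way where the protocol states otherwise, and ±10% is the only window written out.
- **Intent.** SAP Table 7 calls the Day 2 trough predose, so a post-dose draw fails that definition. This stands for Ctrough. It is a parameter definition, though, not a collection rule, and it does not govern AUC0-24.
- **Likelihood.** Subjects are confined, vital signs are due within an hour before each dose, and PK follows vital signs when they coincide. In Part C, expired CO is also predose and ranks after PK. Late draws are therefore unlikely, but not ruled out.
- **Detectability.** Dose times and actual draw times are recorded, so a late draw could be found. No stated rule says what to do with it for AUC0-24.

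A reader might infer that the Day 1 data will be corrupted, or that the DSMB would be misled into escalating. The documents do not support either reading. They give no frequency of late draws. An inflated Day 1 AUC moves towards the exposure limit in Protocol 3.5.2, so it errs on the cautious side. Day 14 AUCτ is untouched because no dose follows. SAP 10 describes interim runs for SAD and MAD only, so its nominal-time rule does not reach Part C, although Protocol 8.6 allows interim PK there.

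**Conclusion.** The point holds as a permitted risk and an inconsistency between protocol and SAP. The stated window allows a Day 1 24-hour draw up to 2.4 h after a Day 2 dose given at about 24 h, while SAP Table 7 presumes a predose draw that no collection rule secures.

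The 2.4 h follows from the documents alone. The consequence is per subject and rests on assumed pharmacokinetics: with ka 1/h and a draw at 25 h, Day 1 AUC0-24 is about 21% to 37% too high for half-lives of 24 to 8 h. Rac(AUC) and effective half-life are biased low, and at the short end effective half-life cannot be computed. With one late subject among eight the effect on the cohort mean is small. It is still worth correcting, because the affected ratios come from small cohorts and the remedy is nearly free.

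**What to change.** 1. In Protocol 6.3, the Table 2 and Table 3 PK footnotes, and SAP Tables 14 and 15, require the Parts B and C Day 1 24-hour sample no more than 60 minutes before the Day 2 dose. This matches Days 7 and 11 to 14 and agrees with SAP Table 7. Keep ±10% for Part A and for the Day 14 post-dose samples, where no dose follows.
2. State that this window prevails over the SOP window, for collection and for the deviation listing in SAP 5.2.
3. In SAP 7.4, set any Day 1 24-hour sample drawn after the Day 2 dose to missing for AUC0-24, Rac(AUC) and Ctrough. Effective half-life then follows from Rac(AUC). It is sensible to apply the same rule to Day 1 AUC0-T and Cmax: in the model above, with a 12- or 24-hour half-life, a 25-hour draw exceeds the first-dose peak.

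The cost is a narrower window for one sample and matching edits in a few places across the two documents. There is no added sample, visit or subject. A subject who is still drawn late would have 12 h as the last usable Day 1 sample.

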## 6.3.1. Pharmacokinetic Sample Processing, Storage and Shipping

Blood samples for PK determination will be processed, stored, and shipped according to the sample processing instructions supplied by the bioanalytical facility.

# 6.3.2. Residual Biological Samples

Plasma samples remaining after the completion of protocol-defined analyses will be retained for potential future metabolite and/or biomarker analysis. No characterization of human genetic material (genes, DNA, RNA) will be performed.

## **6.4.** Smoking Assessments for Part C only

# 6.4.1. Fagerström Test for Cigarette Dependence (FTCD)

The Fagerström Test for Cigarette Dependence (FTCD) is a standardized self-report questionnaire measuring nicotine dependence severity administered at Screening and will be considered a source document. The FTCD will be administered by an Investigator or other individual that is suitably qualified by education or training. See APPENDIX 10 for a sample FTCD.

## 6.4.2. Smoking Time-Line Follow-back (TLFB)

The Smoking Time-Line Follow-back (TLFB) is a standardized method to obtain estimates of daily consumption of tobacco cigarettes using a calendar technique administered at Screening and on Day -1 and will be considered a source document. The Smoking TLFB will be administered by an Investigator or other individual that is suitably qualified by education or training.

Altasciences Project Number: CNO-P5-319

# 6.4.3. Expired Carbon Monoxide (ECO) Level

Expired breath CO will be measured with a Bedfont SmokerlyzerTM at the following timepoints as outlined in Table 3:

- Screening
- Check-in (Day -1)
- At predose on Days 1 to 14

# 6.4.4. Blood Sampling for Cotinine

Blood samples will be collected (1 tube of 3 mL each) to measure plasma cotinine levels at predose on Days 1, Day 7, and Day 14 as outlined in Table 3.

Blood samples will be collected by direct venipuncture into a labeled tube containing the appropriate anticoagulant as specified by the bioanalytical facility. As an option to the subject or if judged necessary by the clinical staff, blood samples may be collected from an indwelling cannula (stylet catheter that requires no flushing), which will be placed in the vein of the subject.

Cotinine concentrations for smoking assessments will be obtained through bioanalysis of the plasma derived from the blood samples drawn during this study, using a validated bioanalytical method.

Bioanalysis procedures will be presented in the bioanalytical plan.

# 6.4.5. Smoking Log

Subjects will be asked to provide sufficient quantity of their usual brand of cigarettes to smoke during their confinement. Subjects will ask for a cigarette from the clinical staff each time they want to smoke. A daily smoking log will be kept to document the number of cigarettes smoked by the subjects from Day -1 to Day 15 as outlined in Table 3.

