#### 3.3.3. Part C - Smoker Phase

Screening of participants will occur within approximately 28 days prior to the first scheduled administration of study medication. Screening data will be reviewed to determine subject eligibility. Subjects who meet all inclusion criteria and none of the exclusion criteria and who consent to participation will be admitted to the CRU for baseline evaluations before dosing (Day -1). All baseline safety evaluation results should be available prior to dosing and continued eligibility confirmed.

Subjects will be randomized to SBP-9330 or placebo in 1 of the 2 planned Smoker cohorts (10 subjects per cohort in 4:1 [SBP-9330:placebo] ratio) to have a total of 8 subjects receiving SBP-9330 and 2 subjects receiving placebo. An additional Smoker cohort (Cohort C3) may be added at the discretion of the Sponsor depending on emerging safety and PK data from previous cohorts.

The proposed Smoker phase design and planned escalation are presented in Table 9.

Cohort	N (active:placebo)	Dose	Drug administrations
C 1	8:2	adaptive	Once daily oral
			administrations for 14
			consecutive days
C2	8:2	adaptive	Once daily oral
			administrations for 14
			consecutive days
Optional C3	8:2	adaptive	Once daily oral
			administrations for 14
			consecutive days

Table 9 Part C - Smoker Phase Design and Dose Levels

Each subject will receive once daily oral administration of the assigned treatment and dose under fasting conditions (SBP-9330 or placebo) for 14 consecutive days.

The Smoker phase of the study may commence after completion of dosing the MAD phase of the study. The Smoker cohort daily dose will be less than or equal to highest MAD dose for which complete safety and PK data are available.

All relevant safety and available plasma PK data will be reviewed by the DSMB before any dose escalation. The DSMB will be provided the randomization code to aide in the review for Part C. The dose levels proposed for Smoker cohorts may be adjusted during the course of the study based on preliminary safety and PK data.

The Smoker phase will have a maximum of 3 cohorts. The number of cohorts may be changed at the discretion of the Sponsor depending on the emerging safety and PK data from the previous cohorts.

Subjects will be confined to the CRU from at least 10 hours prior to drug administration until approximately 48 hours after last study drug administration. Subjects will therefore be confined for 17 days and 16 nights (Day -1 to Day 16).

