## 6.4.6. Minnesota Nicotine Withdrawal Scale (MNWS)

The Minnesota Nicotine Withdrawal Scale (MNWS) is a self-report measure used to monitor symptoms of tobacco withdrawal. The MNWS will be administered by an Investigator or other individual that is suitably qualified by education or training on Day -1 and at 5 hours (±30 minutes) postdose on Days 1 to 14 as outlined in Table 3. The assessment on Day -1 should be completed at approximately the same time as the 5-hour postdose timepoint on dosing days. See APPENDIX 11 for a MNWS example.

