3.1.3 Part C - Smoker Phase

Screening of participants will occur within approximately 28 days prior to the first scheduled administration of study medication. Screening data will be reviewed to determine subject eligibility. Subjects who meet all inclusion criteria and none of the exclusion criteria and who consent to participation will be admitted to the CRU for baseline evaluations before dosing

(Day -1). All baseline safety evaluation results should be available prior to dosing and continued eligibility confirmed.

Subjects will be randomized to SBP-9330 or placebo in 1 of the 2 planned Smoker cohorts (10 subjects per cohort in 4:1 [SBP-9330:placebo] ratio) to have a total of 8 subjects receiving SBP-9330 and 2 subjects receiving placebo. An additional Smoker cohort (Cohort C3) may be added at the discretion of the Sponsor depending on emerging safety and PK data from previous cohorts.

Table 4: Part C - Smoker Phase Design and Dose Levels

Cohort	N(active:placebo)	Dose	Drug administrations
C1	8:2	adaptive	Once daily oral administrations for 14 consecutive days
C2	8:2	adaptive	Once daily oral administrations for 14 consecutive days
Optional C3	8:2	adaptive	Once daily oral administrations for 14 consecutive days

Each subject will receive once daily oral administration of the assigned treatment and dose under fasting conditions (SBP-9330 or placebo) for 14 consecutive days.

The Smoker phase of the study may commence after completion of dosing the MAD phase of the study. The Smoker cohort daily dose will be less than or equal to highest MAD dose for which complete safety and PK data are available.

All relevant safety and available plasma PK data will be reviewed by the DSMB before any dose escalation. The DSMB will be provided the randomization code to aide in the review for Part C. The dose levels proposed for Smoker cohorts may be adjusted during the course of the study based on preliminary safety and PK data.

The Smoker phase will have a maximum of 3 cohorts. The number of cohorts may be changed at the discretion of the Sponsor depending on the emerging safety and PK data from the previous cohorts.

Subjects will be confined to the CRU from at least 10 hours prior to drug administration until approximately 48 hours after last study drug administration. Subjects will therefore be confined for 17 days and 16 nights (Day -1 to Day 16).

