7.5.3 Smoking Assessment (Part C only)

The following data will be assessed for the Safety population of Part C and will be listed and summarized using descriptive statistics:

- Expired carbon monoxide (ECO) level
- Plasma cotinine level
- Number of cigarettes smoked (smoking log)
- Minnesota Nicotine Withdrawal Scale (MNWS) responses
- Questionnaire on Smoking Urges – Brief version (QSU-Brief) responses
-

Actual values and change from baseline will be presented in a listing and will be summarized by Symptoms (if applicable) and visit.

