9.3 Analysis Timepoints

Unless otherwise specified, the baseline value will be defined as the last non-missing evaluation prior to the first dose of study medication.

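### Change from baseline in cigarettes smoked subtracts a part-day Day -1 count from whole-day counts, so the within-arm change is not like-for-like

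*Protocol*

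**What the plan says.** **The log.** Protocol 6.4.5 builds the count from requests made in the unit: "Subjects will ask for a cigarette from the clinical staff each time they want to smoke". It records "the number of cigarettes smoked by the subjects from Day -1 to Day 15". The smoking-log row of Protocol Table 3 has an entry on Day -1 and none at Day 1 predose.

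**The analysis.** For the five smoking endpoints, cigarettes smoked among them, SAP 7.5.3 states: "Actual values and change from baseline will be presented in a listing and will be summarized by Symptoms (if applicable) and visit". SAP 9.3 says that, unless otherwise specified, "the baseline value will be defined as the last non-missing evaluation prior to the first dose of study medication". No exception is given for the log.

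**Arrival.** Protocol 6.4.3 identifies Day -1 as check-in. Protocol 3.3.3 has subjects "confined to the CRU from at least 10 hours prior to drug administration", and SAP 3.1.3 agrees. Neither gives a clock time. Protocol 6.4.6 adds, for the MNWS: "The assessment on Day -1 should be completed at approximately the same time as the 5-hour postdose timepoint on dosing days". Section 6.4.7 has the same rule for the QSU-Brief, and section 5.3 puts dosing in the morning.

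**Restriction on dosing days.** Protocol 4.4 bars smoking from at least 1 hour before to 2 hours after each dose.

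**Another pre-dose measure.** The TLFB (Protocol 6.4.2) gives "estimates of daily consumption of tobacco cigarettes using a calendar technique administered at Screening and on Day -1". SAP 7.5.3 does not use it.

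**Groups.** Smoker cohorts are randomized 8:2 (Protocol 5.2.3). Protocol 8.5 summarizes smoking data by treatment and dose level. The general Part C layout in SAP 9.1 shows each cohort and pooled placebo.

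**The concern.** Under these rules the Day -1 entry is the only log value that can serve as baseline. It omits whatever the subject smoked before arriving, whereas Days 1 to 15 fall wholly within confinement, which runs to Day 16. The subtraction sets part of a day against a whole day. No scaling and no minimum observation time is specified.

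The result is a within-arm change whose size, and possibly sign, depends on an arrival hour that the documents leave open. Protocol 1.1.2 presents the drug as a candidate aid to smoking cessation. A real reduction in an active cohort that shows as no change, or as an increase, could mislead whoever plans the next study.

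**Working it through.** The documents give no effect size, SD or power for this endpoint, so there is no planned figure to reproduce. The check is direct arithmetic.

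**Inputs from the documents:** log baseline on Day -1; dosing on Days 1 to 14; abstention of 3 hours per dose (1 before, 2 after); morning dosing; Day -1 questionnaires at about the clock time of 5 hours post-dose.

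**Assumptions not in the documents:** smoking spread evenly over 07:00-23:00 (16 hours) and dosing at 08:00. The 5-hour point is then 13:00, so arrival is taken as no later than about 13:00.

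**Formulas**, with usual consumption *r* per day and check-in hour *c*:
- Baseline log = *r* × (23 − *c*)/16.
- Post-dose count when smoking is otherwise unchanged: (a) *r*, if the abstention is made up later in the day; (b) *r* × 13/16, if it is not.
- Apparent change = post-dose count ÷ baseline log − 1. This does not depend on *r*.

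| Check-in | Baseline as share of a day | (a) Make-up | (b) No make-up |
|---|---|---|---|
| 08:00 | 15/16 = 0.9375 | +7% | −13% |
| 10:00 | 13/16 = 0.8125 | +23% | 0% |
| 12:00 | 11/16 = 0.6875 | +45% | +18% |
| 13:00 | 10/16 = 0.625 | +60% | +30% |

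**Day 15.** No dose is given, so the abstention offset is absent and column (a) applies to everyone. In a subject who does not make up, the shift jumps between Day 14 and Day 15 with no change in behaviour.

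**Reduction that would read as no change**, check-in 13:00: (a) 1 − 0.625 = 37.5%; (b) 1 − 0.625/0.8125 = 23.1%.

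**Contrast with placebo in the same cohort.** Take 20 per day, check-in 13:00, make-up, and a true 25% reduction on active. The baseline is 20 × 0.625 = 12.5. Active shows 15 − 12.5 = +2.5 and placebo 20 − 12.5 = +7.5. The difference is −5, the true effect.

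A simulation agrees (20,000 runs; mean 18 per day, between-subject SD 5, check-in spread over 10:00-14:00, full make-up, true 25% reduction). Mean within-active change is about +1.1. The contrast on change is −4.6, −4.5 and −4.5 for 8:2, 16:4 and 24:6, the same as the contrast on post-dose counts. At 8:2 the SD of the contrast on change is 4.57, about the size of the effect.

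**Contrast with pooled placebo.** Suppose smoking is unchanged at 20 per day with full make-up, C1 checks in at 10:00 and C2 at 13:00. C1 shows 20 − 16.25 = +3.75, C2 shows 20 − 12.5 = +7.5, and pooled placebo (2 from each) averages +5.625. C1 then differs from pooled placebo by −1.875 and C2 by +1.875, which could pass for a dose difference.

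**The case against.** The strongest reply is that the controlled comparison is sound. Placebo subjects in a cohort share the same Day -1 window, actual values are reported beside change, and the protocol already asks for summaries by treatment and dose. This stands for the same-cohort contrast. It does not repair the within-arm change that the SAP will tabulate, and the same-cohort contrast rests on 2 placebo subjects. Pooling gives 4 to 6, but the artefact cancels only if check-in times are alike across cohorts.

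Size is also open to challenge. From the 10-hour minimum, a reader might infer evening check-in; at 18:00 the same formula gives +220% with make-up. The Day -1 questionnaire timing and morning dosing do not fit that. Nor can one say flatly that unchanged smoking appears as an increase, because the abstention rule can cancel or reverse the shift. Likewise, a true 30% reduction is hidden for check-in after about noon only with full make-up. Without it, smoking falls to 0.7 × 13/16 = 0.569 of usual and reads as −17% against 0.6875 (12:00) or −9% against 0.625 (13:00). These limits are accepted.

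A TLFB baseline has its own fault. It is retrospective self-report of smoking outside the unit. Abstention alone would then give 13/16 − 1 = −19% without make-up, before any effect of confinement. That also stands, and limits how such a score may be read.

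**Conclusion.** The mismatch follows from the documents' own rules: a part-day baseline is subtracted from whole days, and the within-arm change in cigarettes smoked is not like-for-like. On the stated assumptions, the shift for check-in between 10:00 and 13:00 runs from +23% to +60% with make-up smoking and from 0% to +30% without, turning negative for earlier arrival. Day 15 carries the full shift. A real within-arm reduction can be understated or hidden.

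A reader might infer that the comparison with placebo is biased too. Within a cohort it is not, in expectation; it is merely imprecise. The contrast with pooled placebo can be distorted if cohorts check in at different hours.

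The priority is minor. The endpoint is exploratory and descriptive, and Protocol 1.1.2 speaks of exploring the feasibility of the smoking assessments. The sample size is not based on statistical considerations, and no test depends on this endpoint.

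**What to change.** In SAP 7.5.3, state that the Day -1 smoking log is listed but not used as baseline for cigarettes smoked. Make daily counts on Days 1 to 14, by cohort and pooled placebo, the main display. List Day 15 separately, since it has no dosing abstention. This needs no new data and costs a sentence or two. It should be done before database lock or unblinding, because SAP section 9 treats analyses not described by then as post hoc.

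If a change score is kept, use TLFB mean cigarettes per day as baseline, label it as including confinement and dosing-abstention effects shared with placebo, and read it only against placebo. The cost is that TLFB data, described in the protocol as a source document, must be entered in the database, and that the baseline is then recalled outpatient smoking.
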